### **7.11.2 Clinical Laboratory Evaluations**

If the data permit, changes in standard laboratory tests (hematology, urine analysis, blood biochemistry, serum bone metabolism biomarkers) will be summarized using descriptive statistics. And by-subject listing will be provided.

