12.0 MANAGEMENT AND REPORTING OF ADVERSE EVENTS/ADVERSE REACTIONS

12.1 Definitions

Adverse Events

An AE is any untoward medical occurrence in a subject administered a medicinal product and which does not necessarily have to have a causal relationship with this treatment. An AE can therefore be any unfavorable and unintended sign (including an abnormal laboratory finding), symptom, a new disease or worsening in severity or frequency of a concomitant disease, temporally associated with the use of a medicinal product, whether or not the event is considered causally related to the use of the product.

Adverse Reactions

An adverse reaction is an AE for which there is at least a reasonable suspicion of a causal relationship between an AE and a suspected medicinal product.

SAEs

An SAE is defined as any untoward medical occurrence that at any dose:

1. Results in DEATH.
2. Is LIFE THREATENING.
 - The term “life threatening” refers to an event in which the subject was at risk of death at the time of the event; it does not refer to an event that hypothetically might have caused death if it were more severe.
3. Requires inpatient HOSPITALIZATION or prolongation of existing hospitalization.
4. Results in persistent or significant DISABILITY/INCAPACITY.
5. Leads to a CONGENITAL ANOMALY/BIRTH DEFECT.
6. Is an IMPORTANT MEDICAL EVENT that satisfies any of the following:
 - May require intervention to prevent items 1 through 5 above.
 - May expose the subject to danger, even though the event is not immediately life threatening or fatal or does not result in hospitalization.
 - Includes any event or synonym described in the Takeda Medically Significant AE List (Table 12.a).

Table 12.a Takeda Medically Significant AE List

Term	
Acute respiratory failure/acute respiratory distress syndrome	Hepatic necrosis
Torsade de pointes / ventricular fibrillation / ventricular tachycardia	Acute liver failure Anaphylactic shock
Malignant hypertension	Acute renal failure
Convulsive seizure	Pulmonary hypertension
Agranulocytosis	Pulmonary fibrosis
Aplastic anemia	Confirmed or suspected endotoxin shock
Toxic epidermal necrolysis/Stevens-Johnson syndrome	Confirmed or suspected transmission of infectious agent by a medicinal product Neuroleptic malignant syndrome / malignant hyperthermia Spontaneous abortion / stillbirth and fetal death

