### **7.1.3 Definition of Study Visit Windows**

Unless otherwise specified, longitudinal data will be summarized at 3-month intervals, as indicated in Table 1 below. The Months defined below will be applied to both the ENANTONE and follow-up periods. If actual data exceed the limits as defined by Table 1 then the sequence will be carried forward to satisfy the actual data.

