**Table 1 Windowing for longitudinal data**

Month	Target Study Day	Lower (Day)	Upper (Day)
3	91	46	135
6	182	136	225
9	273	226	315
12	365	316	405
15	456	406	495
18	547	496	585
21	638	586	675
24	730	676	765
27	821	766	855
30	912	856	945
33	1003	946	1035
36	1095	1036	1125
39	1186	1126	1215
42	1277	1216	1305
45	1368	1306	1395
48	1460	1396	1485
51	1551	1486	1575
54	1642	1576	1665
57	1733	1666	1755
60	1825	1756	1845

When a subject has multiple usable records within a window then the record nearest the target day will be used, and when two are equal distant from the target day, different days, then the later will be used. Lastly, if multiple values are on the same day then mean value (if numeric data) or the mode (if categorical data) will be used.

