### **7.1.7 Conventions for Missing Other Analysis Dates**

In order to derive 3-month intervals for efficacy or safety analysis, the following methods can be used to impute missing or partial start dates:

- Start date month/year available and day missing:
  - If the month and year are the same as those in the first dose date of ENANTONE treatment or study day -93, then the first dose date or study day -93 is to be used to impute the start date.
  - If the month and/or year are different from those in the first dose date of ENANTONE treatment or study day -93, then first day of the month will be used for the start date.
- Start date year available and month/day missing:
  - If the year is the same as those in the first dose date of ENANTONE treatment or study day -93, then the first dose date or study day -93 is to be used to impute the start date.
  - If the year is not the same as the year of the first dose date of ENANTONE treatment or study day -93, set the start date as January 1.

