### **7.8.3 Additional Efficacy Endpoint(s)**

Percent of patients with a change from baseline in the following parameters will be summarized in a similar manner as the above categorical secondary efficacy endpoint:

- Increase in predicted adult height during and after treatment with ENANTONE
- Change from baseline for BMI
- Change from baseline in BMD
- Change from baseline in patient height

For these and the other additional efficacy endpoints, descriptive statistics will be provided without inferential comparisons for the end of ENANTONE treatment phase and 3-month intervals and follow-up segments previously described.

- Increase in predicted adult height during and after treatment with ENANTONE
- Change from baseline in standard laboratory tests during and after treatment with ENANTONE
- Incidence rate of polycystic ovarian syndrome during and after treatment with ENANTONE
- Evaluation of long term effect on reproduction
- Change from baseline for BMI

- Change from baseline in BMD
- Change from baseline in patient height

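### Laboratory safety is summarised only as raw change from one record per 3-month window, so transient abnormal results can miss the by-time tables and none is counted as abnormal

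*SAP*

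**What the plan says.** SAP 7.11.2 gives the whole laboratory plan: "If the data permit, changes in standard laboratory tests (hematology, urine analysis, blood biochemistry, serum bone metabolism biomarkers) will be summarized using descriptive statistics". It adds: "And by-subject listing will be provided".

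SAP 7.8.3 lists the same outcome, "Change from baseline in standard laboratory tests during and after treatment with ENANTONE", among endpoints described "for the end of ENANTONE treatment phase and 3-month intervals and follow-up segments previously described". SAP 7.8.1 defines end of treatment, for the primary endpoint, as the last observation in the treatment phase.

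SAP 7.1.3 sets the default: "Unless otherwise specified, longitudinal data will be summarized at 3-month intervals, as indicated in Table 1 below". The first Table 1 window runs from Day 46 to Day 135. Under the table: "When a subject has multiple usable records within a window then the record nearest the target day will be used". A tie goes to the later record, and several numeric values on one day are averaged. SAP 7.1.7 shows that safety data are meant to go into these intervals: "In order to derive 3-month intervals for efficacy or safety analysis, the following methods can be used to impute missing or partial start dates". SAP 7.11.2 makes no exception.

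SAP 7.1.1 defines change as post-baseline minus baseline. SAP 7.1 requires number, mean, SD, median, minimum and maximum. SAP Table 2 gives abnormality limits for four hormones only. Protocol 10.2.2.12 says that results are recorded and does not mention reference ranges.

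**The concern.** Taking the record nearest the target day is sensible for a trend over time. Laboratory safety asks something else: how many children had an abnormal value at any time on treatment. The plan has no table that answers this.

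Two routes lead out of the by-time tables. A result on Days 2 to 45 belongs to no window. A later abnormal result is set aside if a repeat in the same window lies nearer the target. In routine care an abnormal result is itself a common reason for a repeat, so having a second record in the window may depend on the value of the first. A result lost in either way remains only in the listing, or as an adverse event if the physician recorded one.

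A value that is kept enters a mean, a median and a range of change. Nothing says how many children crossed a limit. Change is also not set against an age and sex reference, although the children are followed for at least 9 months while they grow. At stake is a named outcome in a study whose first objective is safety.

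**Working it through.** **1. Table 1 reproduced.** Window k has lower limit 90k − 44, upper limit 90k + 45 and target equal to the whole part of 365k/4. All 20 printed rows match, with no gap or overlap between windows. The first opens on Day 46, so Days 2 to 45 (44 days) have none.

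**2. Length of a 9-month phase.** 9 × 30.44 = 273.96, rounded to 274, so the last dose falls on Day 275. SAP 7.1 adds 45 days unless another GnRH agonist starts earlier: 275 + 45 = Day 320. Days 2 to 320 are 319 days.

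**3. When a repeat displaces an abnormal result.** Let the abnormal result fall on day d and the repeat on day d + r, in a window with lower limit L and target T. The repeat is used if |d + r − T| ≤ |d − T|, that is, if d ≤ T − r/2. Displaced days per window = whole part of (T − r/2) − L + 1.

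| Repeat after | Month 3 (L 46, T 91) | Month 6 (L 136, T 182) | Month 9 (L 226, T 273) | Displaced | Plus 44 without a window | Share of 319 |
|---|---|---|---|---|---|---|
| 7 days | 87 − 46 + 1 = 42 | 178 − 136 + 1 = 43 | 269 − 226 + 1 = 44 | 129 | 173 | 54% |
| 14 days | 84 − 46 + 1 = 39 | 175 − 136 + 1 = 40 | 266 − 226 + 1 = 41 | 120 | 164 | 51% |
| 28 days | 77 − 46 + 1 = 32 | 168 − 136 + 1 = 33 | 259 − 226 + 1 = 34 | 99 | 143 | 45% |

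Days 316 to 320 lie in the Month 12 window, but a repeat 7 or more days later falls after the phase, so none is displaced there.

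Assumptions: every abnormal result is repeated once after the stated interval, the repeat is normal, and abnormal results are spread evenly over the days. The documents give none of these.

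**4. End-of-treatment summary.** It takes the last observation, not the one nearest a target. It shows an abnormality that is late or persists. It does not recover a result that was repeated within the phase, because that result is then not the last.

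**5. Regular testing instead.** Testing frequency is not fixed, so a range is assumed. The figures are results that reach a by-time table (windows plus end of treatment).

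| Schedule | 9-month course | 36-month course |
|---|---|---|
| 4-weekly | 4/11 (36%) | 13/40 (33%) |
| 8-weekly | 3/5 (60%) | 12/20 (60%) |
| 12-weekly | 3/3 | 12/13 (92%) |
| 3-monthly | 3/3 | 12/12 |

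For 4-weekly tests over 9 months, the windows select Days 85, 169 and 281, and end of treatment adds Day 309.

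**6. Growth.** The documents give no age-related drift for any test. With an assumed drift g of 0.05 to 0.5 SD per year and an assumed drug effect e of 0.2 to 0.5 SD in the same direction, growth's share of the mean change after m months is (gm/12) / (gm/12 + e). At 9 months this runs from 0.0375/0.5375 = 7% to 0.375/0.575 = 65%. At 36 months it runs from 0.15/0.65 = 23% to 1.5/1.7 = 88%.

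**The case against.** The case for the plan is substantial:

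- **Selection goes by day, not value.** On a fixed schedule this does not bias mean change. That stands. It does not cover repeats that were prompted by the result.
- **Extremes are visible.** Minimum and maximum change are shown. If one child in 100 goes from 20 to 200 U/L on ALT (assumed values), the mean moves by only 180/100 = 1.8 U/L, but the maximum shows +180. That stands for a value that was kept. A maximum still gives no number of children affected and no position against a reference range.
- **Other outlets exist.** The listing is not restricted to selected records. Protocol 12.1 lets an abnormal laboratory finding be an adverse event, and the adverse event tables cover Days 1 to 45. Both points stand. A listing gives no percentage, however, and the adverse event tables depend on what the physician wrote down.
- **Priority.** This is an additional outcome, planned only if data permit; the primary safety outcome is adverse event incidence. That limits the weight of the point.
- **Reference ranges.** They are not listed as collected, so a fix built only on shift tables might not be workable. That stands and shapes the fix.

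A reader might infer that growth dominates the laboratory change. The documents give no figure for it, and the assumed range in the working runs from minor to dominant. SAP 7.8 also presents its endpoints by sex, although SAP 7.11 by default does not stratify safety by sex.

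**Conclusion.** The point holds as a gap in the summary. No planned table counts abnormal laboratory values at any time, and the default windowing can leave a transient abnormal result out of the by-time tables. Under the assumptions in step 3, 45% to 54% of such results in a 9-month course reach no 3-month interval.

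A reader might take this to mean that about half of all abnormal values vanish. The documents do not support that. The shares apply only to results that are always retested and then normal. They also depend on the span counted: stopping at Day 274 gives 63%, 58% and 48%, but leaves out Days 275 to 320, on which no result is displaced. With about one test per window after Day 45 nothing is lost, and a persistent abnormality stays in the tables.

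That growth may be mixed with drug effect stands as a risk of unknown size.

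**What to change.** In SAP 7.11.2, exempt safety laboratory data from the Table 1 record-selection and same-day averaging rules for an any-time summary:

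1. For each parameter and phase, report the highest and lowest post-baseline value from all records, including Days 1 to 45 and repeat tests, with the change to each, by dose group and overall.
2. Where the laboratory report's reference range is available, or a paediatric age and sex range named in advance is applied, add a shift table from baseline category to worst category, with number and percentage of subjects.
3. Keep the planned change summaries, and state that change in ALP and bone markers is not adjusted for age.

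Item 1 needs only results that the protocol already has recorded. Item 2 needs reference ranges to be entered, from eight sites over an index period of 1998 to 2018, or one external range to be chosen and named. The other cost is a set of extra tables.

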### **7.11.3 Vital Signs**

All Vital Signs results will be presented in data listings.

### **7.11.4 12-Lead ECGs**

All ECG results will be presented in data listings.

### **7.11.5 Other Observations Related to Safety**

The physical examination findings and vaginal bleeding (females) growth rate, weight, cranial CT/MRI will be presented in data listings.

## **7.12 Interim Analysis**

Not Applicable.

## **7.13 Changes in the Statistical Analysis Plan**

The statistical analysis in the protocol anticipated sufficient subject numbers to permit the comparing of Low and High dose levels of ENANTONE. At the time of finalizing the SAP it was determined that these types of analyses wouldn't be feasible. Therefore, the proposed Cochran-Mantel-Haenszel test will be omitted.

